## **3.3 General Considerations**

The principal analyses outlined in this SAP will be conducted by Fortrea, in accordance with the contract with AstraZeneca (AZ) AB and following the Excellence in Medical Partnership for Outsourced Worldwide Evidence Research (EMPOWER) description of services.

The general principles below will be followed for analyses:

Descriptive statistics will be used for all variables, as appropriate. Continuous variables will be summarised by the number of observations, mean, standard deviation (SD), median, Q1, Q3, minimum and maximum. For log-transformed data, it is more appropriate to present geometric mean, coefficient of variation (CV), median, minimum and maximum.

Categorical variables will be summarised by frequency counts and percentages for each category.

For qualitative variables, the number (n) and percentage (%) of subjects with non-missing data per category will be the default summary presentation, and where appropriate and present, the number of missing values as a “Missing” category. Number of subjects in the analysis population will be used as denominator for percentages calculation, unless stated otherwise in TFLs mock shell(s).

For continuous data, the mean and median will be rounded to 1 additional decimal place compared to the original data. The standard deviation will be rounded to 2 additional decimal places compared to the original data. Minimum and maximum will be displayed with the same accuracy as the original data.

For categorical data, percentages will be rounded to 1 decimal place.

SAS® version 9.3 or higher will be used for all analyses

It is acceptable to present large numerical values in more appropriate units. For example, an Area Under Curve (AUC) value of 123,000 ng h/mL may be reported as 123 µg h/mL instead. It is however, important to keep the units consistent within the report and the precision consistent with that prior to conversion.

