### 4.6.2.2 Presentation

#### AE Summary

An overall summary table of the number of participants experiencing each category of AEs will be produced using the SSO and SSR. Analyses using the SSO will be restricted to AEs which occurred during the inpatient period and will be presented overall. Analyses using the SSR will include all AEs and will be presented by treatment group received during the outpatient period and overall.

Any AE occurring within 7 days of the discontinuation of investigational product will be included in the AE summaries. Treatment emergent adverse events (TEAEs) occurring prior to first dose of investigational product (i.e. before study day 1) which subsequently worsen in severity following dosing will be presented in the summary tables. All other AEs occurring prior to first dose of investigational product (i.e. before study day 1) or more than 7 days after the discontinuation of investigational product will be listed separately, but not included in the summaries.

An overview table will summarize the number and percentage of participants with at least one of the following AEs, where participants with more than one AE in a particular category are counted only once in that category, as well as the absolute counts of number of AEs. In the overall summary table for the SSO, no event rate will be displayed. In the overall summary table for the SSR, the event rate, per 100 patient years, will be displayed. This will be calculated as the number of participants with at least one AE (in either inpatient or outpatient phase) divided by the total time at risk (i.e. time from first dose of SZC during the inpatient phase to date of study discontinuation) across all participants in given group, multiplied by 365.25 multiplied by 100.

- Any AEs
- Any AEs with outcome of death
- Any SAEs (including events with outcome of death)

- Any AEs leading to treatment discontinuation

Number of participants with AEs

The number and percentage of participants reporting each AE and the absolute count of AEs will be summarised by system organ class (SOC) and preferred term (PT). Tables will be sorted by international order for SOC and PTs will be sorted alphabetically. The following summaries will be produced using the SSO and SSR:

- AEs;
- Most common AEs (>5% in any treatment group);
- AEs by relationship to treatment;
- AEs by maximum intensity;
- AEs leading to treatment discontinuation;
- SAEs;
- SAEs related to treatment;
- AEs leading to death;

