#### **4.6.7.2 Presentations**

ECG data will be summarised and listed. Absolute and change from baseline in ECG parameters will be summarised at each scheduled timepoint. The continuous ECG parameters will be summarised with descriptive statistics. If a participant has multiple results for a particular test at a particular time point, the result selected per rules in section 3.3.2 will be used for the summary. These will be provided for the SSO, limited to visits during the inpatient period and presented overall, and the SSR, which will include all visits with ECG assessments and be presented by treatment received during outpatient period.

All summaries of ECG data will exclude observations from site 7001 where a serious breach in the collection of ECG results was identified.

The number and percentage of participants with QTcF results exceeding ICH boundaries ( $>450$ ms,  $>480$ ms,  $>500$ ms), with increases from baseline  $>30$ ms,  $>60$ ms,  $>90$ ms, decreases from baseline  $>30$ ms,  $>60$ ms,  $>90$ ms and for each combination of post-baseline values ( $>450$ ms,  $>480$ ms,  $>500$ ms) and increases ( $>30$ ms,  $>60$ ms,  $>90$ ms) will be presented for the SSO, limited to visits during the inpatient period and presented overall, and the SSR which will include all visits with scheduled ECG assessment and be presented by treatment received during the outpatient period. Participants are included based on maximum QTcF value and are counted in all cumulative categories (e.g., a participant with a QTcF value of 510ms would be included in 450ms, 480ms and 500ms rows).

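### The adverse event rate per 100 patient-years in SAP 4.6.2.2 is neither an event rate nor a first-event incidence rate, and it reads low against both

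*SAP*

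**What the plan says.** SAP 4.6.2.2 states: "In the overall summary table for the SSR, the event rate, per 100 patient years, will be displayed". The overview table has four rows: any AE, AEs with outcome of death, SAEs, and AEs leading to treatment discontinuation.

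- **Numerator.** The rate is "calculated as the number of participants with at least one AE (in either inpatient or outpatient phase) divided by the total time at risk". The same section says that "participants with more than one AE in a particular category are counted only once in that category".
- **Denominator.** Time at risk is the "time from first dose of SZC during the inpatient phase to date of study discontinuation", summed over all participants in the group. Nothing ends a participant's time at the first AE.
- **Counting window.** AEs that occur "more than 7 days after the discontinuation of investigational product will be listed separately, but not included in the summaries". SAP 4.6.2.1 and Protocol 9.4.4 use the same 7-day limit to define a treatment-emergent AE.
- **Follow-up after stopping.** Under Protocol 7.1.1, a participant who permanently stops study intervention is still followed according to the Schedule of Activities.

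The same overview table also gives the number and percentage of participants with an AE, and the absolute number of AEs.

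**The concern.** A rate needs a numerator and denominator that belong together. If each participant can count only once, time at risk should end when that participant counts. If time runs over the whole follow-up, every event should count. The SAP pairs a once-only count with the whole follow-up, so the result is neither of the two standard rates, although it is labelled an event rate over time at risk.

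There is a second mismatch. The numerator closes 7 days after investigational product is stopped, while the denominator runs to study discontinuation. Both mismatches lower the figure. A reader of the study report would take it as a standard event rate or incidence rate, and would be furthest out in the any-AE row, where the proportion affected is likely to be highest.

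**Working it through.** The documents give no AE proportion and no numerical rate, so there is no stated figure to reproduce. The check compares the SAP formula with the two standard rates.

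**Inputs**
- Follow-up: about 180 outpatient days plus 7 follow-up days (Protocol 1.1), and 1 to 21 in-hospital days, so about 188 to 208 days. I use T = 194, which assumes 7 in-hospital days.
- p = the share of participants with at least one AE in the row. This is an assumption, varied from 5% to 80%.
- Constant hazard and complete follow-up, both assumptions.

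**Against a first-event rate**
- SAP figure = p / T × 36,525 (T in days).
- First-event rate: the expected time to first AE or end of follow-up is p/λ per participant, so the rate is λ = −ln(1 − p) / T × 36,525.
- Ratio SAP / first-event = p / (−ln(1 − p)). T cancels, so the in-hospital stay does not affect the relative shortfall.

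Example at p = 50%: 0.5/194 × 36,525 = 94.1, against 0.6931/194 × 36,525 = 130.5. The ratio is 0.721, or 28% low.

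| p | SAP, per 100 PY | First-event, per 100 PY | Ratio |
|---|---|---|---|
| 5% | 9.4 | 9.7 | 0.975 |
| 10% | 18.8 | 19.8 | 0.949 |
| 20% | 37.7 | 42.0 | 0.896 |
| 40% | 75.3 | 96.2 | 0.783 |
| 50% | 94.1 | 130.5 | 0.721 |
| 60% | 113.0 | 172.5 | 0.655 |
| 80% | 150.6 | 303.0 | 0.497 |

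A simulation at p = 60% gave 113.0 and 172.7, in agreement.

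The constant hazard sets the size but not the direction. If every first AE fell on the last day, the ratio would be 1. If every one fell on the first day, person-time to first AE would be (1 − p)T and the ratio 1 − p. At p = 50% the ratio therefore lies between 0.5 and 1.

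For AEs with outcome of death, follow-up ends at death. Little time can accrue after the event, so this shortfall is close to nil.

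**Against an event rate**

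If affected participants have k AEs each on average, events over the same time equal k × p / T. The SAP figure is then 1/k of the event rate: equal at k = 1, half at k = 2. The documents do not give k.

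**Counting window**

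Take an Arm A participant who stops SZC at outpatient day 60 and stays in the study to day 187 (180 + 7). AEs are included up to day 67, but time runs to day 187, so 187 − 67 = 120 days are added in which no AE can be counted. How often this happens is not in the documents, so I do not size it overall.

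**The case against.** The strongest reply is that the SAP defines the measure openly. Participants with an event over total follow-up is a usable crude figure, and the table also shows n, % and AE counts. Safety carries no hypothesis (Protocol 1.1) and is generally reported descriptively (Protocol 9.4.4), so no test or decision rests on the rate. All of this stands and limits the seriousness. It does not make the label correct.

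Four stronger readings are tempting, and the documents do not support them.

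- **The between-arm ratio is misreported.** With equal follow-up, the ratio of the two SAP figures is the risk ratio. For 80% against 50% it is 0.80/0.50 = 1.60, where the hazard ratio would be ln(0.2)/ln(0.5) = 2.32. These are two different measures, and the risk ratio is a valid contrast.
- **This is the only time-adjusted safety information.** That is so within the AE tables. But death and all-cause admission enter the time-to-event analysis in SAP 4.2.3, and admission counts are modelled with a time offset in SAP 4.2.5.4.
- **Arm B's rate is distorted more than Arm A's by the 7-day limit.** Read literally, study SZC ends at discharge in Arm B, so the numerator would close early there. But the SAP does not say what discontinuation of investigational product means in Arm B, and 4.6.2.2 also says the SSR analyses include all AEs. A difference between arms cannot be established.
- **QTcF percentages are understated because of site 7001.** SAP 4.6.7.2 says: "All summaries of ECG data will exclude observations from site 7001 where a serious breach in the collection of ECG results was identified". It gives no denominator for the QTcF categories. SAP 3.3 defaults to the analysis-set size, but yields to mock shells that are not among the documents and also refers to participants with non-missing data. The site's size is not given; an average site would hold 130/50 = 2.6 to 130/30 = 4.3 of about 130 randomised participants, or 2% to 3.3%. This is missing detail, not an error.

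**Conclusion.** The point holds for the AE rate. The planned figure cannot exceed either standard rate and will usually lie below both. Against a first-event rate the shortfall depends on the row: about 5% if 10% of participants have the event, 28% at 50%, 50% at 80%, and close to nil for AEs with outcome of death. These sizes rest on assumed AE proportions, a constant hazard and complete follow-up; the direction does not. Time beyond the counting window lowers the figure further, by an amount the documents do not allow one to compute.

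This is a defect in how a descriptive safety measure is defined and named. It does not touch the efficacy analyses or the AE counts and percentages. The site 7001 QTcF matter is at most a request for clarification.

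**What to change.** In SAP 4.6.2.2, choose one of the following and label it accordingly.

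1. **Event rate:** total number of AEs in the category divided by person-time within the AE counting window. The counts are already produced for this table.
2. **Exposure-adjusted incidence rate:** participants with at least one AE in the category divided by person-time that ends at the first AE of that category or at the end of the counting window, whichever comes first.

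Either option needs the end of the counting window stated for each arm, including Arm B. The cost is a wording change and minor table reprogramming, with no new data. The printed rates will be higher than under the present formula.

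Optionally, 4.6.7.2 could state that the QTcF percentages use participants with an included QTcF value as denominator.

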#### **4.6.3 Clinical Laboratory, Blood Sample**

##### **4.6.3.1 Definitions and Derivations**

Absolute change from baseline in haematology and clinical chemistry variables will be calculated for each post-dose visit.

##### **4.6.3.2 Presentations**

Laboratory data (clinical chemistry and haematology) will be summarised and listed. Laboratory data outside the reference ranges will be indicated in the listings. If a participant has multiple results for a particular test at a particular time point, the rules of section 3.3.2 will be followed. System international (SI) units will be reported for all analytes.

Laboratory data absolute and change from baseline values for continuous chemistry and haematology parameters will be summarised at each scheduled assessment time. Separate tables will be provided for the SSO, restricted to visits during the inpatient period and presented overall and for the SSR, which will include all visits and be presented by treatment received during the outpatient period.

#### **4.6.4 Clinical Laboratory, Urinalysis**

##### **4.6.4.1 Definitions and Derivations**

The following urinalysis parameters will be presented: U-hb/Erthrocytes/Blood, U-protein/Albumin, U-Glucose.

##### **4.6.4.2 Presentations**

Shift tables will be presented where shift from baseline to the maximum value will be summarised. These will be provided separately for the SSO, which will be limited to visits during the inpatient period, and the SSR, which will summarize the worst overall value across all visits.

#### **4.6.5 Other Laboratory Evaluations**

##### **4.6.5.1 Definitions and Derivations**

Not Applicable.

##### **4.6.5.2 Presentations**

Not Applicable.

#### **4.6.6 Vital Signs**

##### **4.6.6.1 Definitions and Derivations**

Vital signs will be evaluated and assessed at screening, the start of the inpatient period, at randomization and all further study visits according to the SoA, Tables 1 of the CSP. Vital signs include height (cm, visit 1 only), weight (kg), pulse rate (beats per minute), systolic blood pressure (mmHg) and diastolic blood pressure (mmHg). Absolute change from baseline will be calculated for each post-dose visit.

##### **4.6.6.2 Presentations**

Vital sign values will be summarised and listed. Vital sign data absolute and change from baseline will be summarised at each scheduled timepoint. The continuous vital sign parameters will be summarised with descriptive statistics. If a participant has multiple results for a particular test at a particular time point, the result selected by the rules in section 3.3.2 will be used for the summary. These will be provided for the SSO, limited to visits during the inpatient period and presented overall, and the SSR, which will include all visits with scheduled vital sign assessment and be presented by treatment received during the outpatient period.

#### **4.6.7 Electrocardiogram**

##### **4.6.7.1 Definitions and Derivations**

Electrocardiogram (ECG) assessments will be performed at screening, randomization, visit 4, visit 7, EOT, and follow-up (as specified in the SoA), and according to clinical

judgement in connection with severe hypokalaemia ( $K^+ < 3.0$  mmol/L), severe hyperkalaemia ( $K^+ > 6.0$  mmol/L) or any symptoms or clinical events suggesting cardiac arrhythmia. ECG parameters will include heart rate (beats/min), PR interval (msec), RR interval (msec), QRS duration (msec), QT interval (msec) and QTcF interval (msec). The absolute change from baseline will be calculated for each post-dose visit.

#### **4.6.7.2 Presentations**

ECG data will be summarised and listed. Absolute and change from baseline in ECG parameters will be summarised at each scheduled timepoint. The continuous ECG parameters will be summarised with descriptive statistics. If a participant has multiple results for a particular test at a particular time point, the result selected per rules in section 3.3.2 will be used for the summary. These will be provided for the SSO, limited to visits during the inpatient period and presented overall, and the SSR, which will include all visits with ECG assessments and be presented by treatment received during outpatient period.

All summaries of ECG data will exclude observations from site 7001 where a serious breach in the collection of ECG results was identified.

The number and percentage of participants with QTcF results exceeding ICH boundaries ( $>450$ ms,  $>480$ ms,  $>500$ ms), with increases from baseline  $>30$ ms,  $>60$ ms,  $>90$ ms, decreases from baseline  $>30$ ms,  $>60$ ms,  $>90$ ms and for each combination of post-baseline values ( $>450$ ms,  $>480$ ms,  $>500$ ms) and increases ( $>30$ ms,  $>60$ ms,  $>90$ ms) will be presented for the SSO, limited to visits during the inpatient period and presented overall, and the SSR which will include all visits with scheduled ECG assessment and be presented by treatment received during the outpatient period. Participants are included based on maximum QTcF value and are counted in all cumulative categories (e.g., a participant with a QTcF value of 510ms would be included in 450ms, 480ms and 500ms rows).

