### **3.3.1.1 Screening / Baseline Period**

For all subjects, the screening period is defined as the period from informed consent to the first dose of SZC. For some variables, data from more than one assessment within the screening period may be collected prior to the first dose of SZC.

The baseline value for a variable is therefore defined as the last non-missing observation before the first dose of study treatment (SZC) in the inpatient period. For assessments on the day of first dose, where time is not captured, a nominal pre-dose indicator, if available, will serve as sufficient evidence that the assessment occurred prior to first dose. Any observation made after the first dose of study treatment will be considered post-baseline.

Assessments on the day of the first dose when neither time nor a nominal pre-dose indicator are captured will be considered prior to the first dose if such procedures are required by the protocol to be conducted before first dose.

In all quantitative summaries from baseline, absolute changes from baseline will be calculated as the post-baseline value minus the value at baseline. The percentage change from baseline will be calculated as  $[(\text{post-baseline value} - \text{baseline value}) / \text{baseline value}] \times 100$ .

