#### **Inpatient Period**

The inpatient period refers to the period from the date of first study intervention dispensation of SZC until the date of randomisation at discharge (exclusive) or until 21 days after the first dose of SZC for participants who have not been randomised.

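### The SAP's single maximum-QTcF selection rule also governs the decrease-from-baseline rows, so the SSR table undercounts participants with a QTcF decrease

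*SAP*

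**What the plan says.** SAP 4.6.7.2 describes one QTcF category presentation with four groups of rows: values above 450, 480 and 500 ms; increases of more than 30, 60 and 90 ms; "decreases from baseline" at the same three thresholds; and combinations of post-baseline value with increase. The sentence that follows sets the selection rule: "Participants are included based on maximum QTcF value and are counted in all cumulative categories". It makes no exception for the decrease rows. Its only example concerns absolute values: "a participant with a QTcF value of 510ms would be included in 450ms, 480ms and 500ms rows".

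The table is produced for the SSO, limited to inpatient visits and shown as one group, and for "the SSR which will include all visits with scheduled ECG assessment", shown by treatment received. SAP 4.6.7.1 says that ECG "assessments will be performed at screening, randomization, visit 4, visit 7, EOT, and follow-up". SAP 3.3.1.1 defines baseline as "the last non-missing observation before the first dose of study treatment (SZC) in the inpatient period", which for the ECG schedule is the screening value. That leaves up to five scheduled post-baseline ECGs on the SAP's list.

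**The concern.** A participant's largest decrease is the lowest post-baseline value minus baseline. Selecting the highest value picks the reading least likely to show a decrease. Under the rule as written, one post-baseline ECG at or near baseline removes the participant from every decrease row, however low the other readings were.

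The sponsor chose to report decreases per participant. If the SSR rows are built this way, their counts will be too low, and a reader of that table alone could take low counts as evidence that QTcF shortening was rare.

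**Working it through.** The plan states no figure here, so there is nothing to reproduce. The check has a logical part and an illustration of size.

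**Logic.** Let B be baseline, X1 to Xk the post-baseline values and t the threshold.
- From the maximum, counted if max(X) − B < −t. This requires every Xj to be more than t below B.
- From the minimum, counted if min(X) − B < −t. This requires at least one Xj to be more than t below B.
- With k = 1 the two rules are identical. With k > 1 the maximum rule can only count fewer participants.

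Example: B = 450 ms; post-baseline 455, 380, 445, 440, 448 ms. The maximum gives 455 − 450 = +5 ms, so no decrease is counted. The minimum gives 380 − 450 = −70 ms, which belongs in the >30 and >60 ms rows.

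**Number of ECGs.** In the SSR, k is up to 5: randomisation, visit 4, visit 7, EOT and follow-up (SAP 4.6.7.1). In the SSO, the inpatient period of a randomised participant ends before the randomisation date (SAP 3.3.1.2). There are then no scheduled post-baseline ECGs, or one if the discharge-day ECG is counted, so k ≤ 1 and nothing scheduled is lost.

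**Size.** Assumptions not in the documents: independent normal readings with within-participant SD s, and mean shift m after baseline (negative for a fall). With φ and Φ the standard normal density and distribution function:
- P(counted from maximum) = ∫ φ(z) Φ(z − (t + m)/s)^k dz
- P(counted from minimum) = 1 − ∫ φ(z) [1 − Φ(z − (t + m)/s)]^k dz

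Results for a decrease over 30 ms (t = 30):

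| k | s (ms) | m (ms) | From maximum | From minimum |
|---|---|---|---|---|
| 5 | 12 | 0 | 0.1% | 13% |
| 5 | 15 | 0 | 0.4% | 24% |
| 5 | 20 | 0 | 1.2% | 39% |
| 5 | 15 | −10 | 1.8% | 44% |
| 5 | 15 | −30 | 17% | 83% |
| 5 | 15 | −50 | 56% | 98% |
| 2 | 15 | 0 | 2.3% | 13% |
| 1 | 15 | 0 | 7.9% | 7.9% |

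The −30 ms row can be checked by hand. When the shift equals the threshold, the five values (each plus 30) and the baseline are exchangeable. The baseline is therefore the largest of six with probability 1/6 = 16.7% (maximum rule) and is not the smallest with probability 5/6 = 83.3% (minimum rule), whatever the SD. The share missed is 1 − 16.7/83.3 = 80%.

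Over SD 10 to 30 ms and shifts of 0 to −30 ms, simulation with k = 5 put the share missed by the maximum rule at 80% to 100% for decreases over 30 ms and 94% to 100% for decreases over 60 ms.

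**The case against.** The strongest reply is that the maximum sentence was meant only for the absolute-value and increase rows. The 510 ms example concerns absolute values, and the phrase about cumulative categories explains nested thresholds. That may have been the intention. It does not remove the problem, because no other participant-level rule is given for the decrease rows: read literally the rule is wrong for them, and read narrowly it is missing. The worst-value rule in SAP 3.3.2 does not fill the gap, since it works within a visit window and gives no direction for QTcF.

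Second, decreases are not hidden from the report. The same section summarises change from baseline at each scheduled timepoint and lists the data, and SAP 3.3 includes the minimum among the continuous summaries. This stands, and it limits the harm. Those outputs do not, however, give the per-participant count that the category table promises.

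Third, the no-shift scenarios measure noise: the lowest of five readings against a single baseline will often fall by over 30 ms by chance. This also stands. Those rows show that the two rules differ, not that real shortening would be missed.

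A reader might infer three stronger things that the documents do not support:
- That the SSO table is affected in the same way. It has at most one scheduled post-baseline ECG for randomised participants. Only additional ECGs could differ, such as clinically triggered ones or the early-discontinuation ECG in the protocol's Schedule of Activities. It also has no arms to compare.
- That the SSR decrease rows will be near zero whatever the data show. A large, sustained fall would appear: 17% are counted with a uniform 30 ms fall and 56% with 50 ms, at SD 15 ms.
- That nearly all decreases are lost as a matter of fact. The share depends on the assumed SD, the shift and the number of ECGs each participant has.

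**Conclusion.** The point holds for the SSR table. As written, SAP 4.6.7.2 counts a decrease only when all of a participant's post-baseline ECGs are below baseline by more than the threshold, and so undercounts decreases substantially. That direction follows from logic alone; the size rests on assumed SDs, shifts and independence of readings. With five ECGs, the illustration runs from 0.1% to 1.2% counted against 13% to 39% (SD 12 to 20 ms, no shift, chance variation only) to 17% against 83% (uniform 30 ms fall). Participants with fewer ECGs lose less.

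The consequence is small. The table is descriptive, no efficacy test or sample size depends on it, and the protocol's QTc exclusion and discontinuation criteria concern prolongation. It is worth correcting because a stated rule gives a wrong count and the correction is easy.

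**What to change.** Replace the selection sentence in SAP 4.6.7.2 with one saying that absolute-value, increase and combination rows use each participant's maximum post-baseline QTcF, and that decrease rows use the minimum post-baseline QTcF, that is, the largest decrease from baseline. It would help to state in SAP 3.3.2 which direction counts as worst for QTcF when a window holds more than one ECG, so that a low reading is not dropped before the minimum is taken.

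A footnote could say that the largest of several decreases from a single baseline includes chance variation, so the arms should be compared with each other rather than with zero.

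The cost is one SAP sentence, an optional clarification and a small programming change. No new data are needed.
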